3.2 Clinical Experience

Medical Uses of Progesterone

Progesterone has been in clinical use since 1934 and was ranked as 189th most prescribed medication in the United States in year 2016 with more than 3 million prescriptions ([https://en.wikipedia.org/wiki/Progesterone_\(medication\)#Medical_uses](https://en.wikipedia.org/wiki/Progesterone_(medication)#Medical_uses)). Progesterone is currently being used in hormone therapy, pregnancy support, fertility support, birth control and gynecological disorders. In hormone replacement therapy, progesterone is used specifically to provide endometrial protection against unopposed estrogen-induced endometrial hyperplasia and cancer in women with intact uteruses [Archer et al. 2019; Kuhl 2005]. The current literature on the role of progesterone in health and disease is now immense, so much is known about its safety and pharmacologic parameters in a wide variety of disorders, including those of the central nervous system. For example, a quick search on just progesterone and inflammation on PubMed, reveals about 1500 papers. For research using progesterone in brain injury the number is 470. Searching for progesterone use on *Clinicaltrials.gov* showed that there are over 1450 trials listed. Of the first 450 trials listed, most address women's health issues such as IVF, prevention of premature birth, menstrual cramps, and infertility among others. However, other trials have tested progesterone for nicotine dependence, tobacco use disorder, endometrial polyps, reduce cannabis dependence, cocaine abuse, acute hemorrhagic stroke, endometrial cancer treatment, polycystic ovary syndrome, night sweats, concussion, alcohol dependence, post-traumatic stress disorder, congenital heart disease, embryo preservation, epilepsy, preeclampsia, bulimia nervosa, recurrent or persistence endometrial carcinoma, postmenopausal sleep disorders, postpartum depression,, and bipolar disorder. There is unequivocal evidence that progesterone is safe as demonstrated by its current clinical uses and the fact that FDA has approved a number of clinical trials with progesterone in highly vulnerable populations with a variety of very dangerous as often deadly illnesses.

Route of Administration for Progesterone

Based on the above discussion, progesterone clearly has a range of medicinal effects including, in particular, anti-GBM activity in different disease models. To test whether progesterone is effective at treating glioblastomas, we need to find a means of dosing patients to achieve high systemic levels using a convenient and easy route of administration. Progesterone has been given in a number of ways including orally, through mucosal surface absorption (e.g. vaginal or rectal administration) or via injection (eg. intramuscular or subcutaneously administration). While oral administration is very convenient and an FDA-approved oral capsule form of progesterone is available (eg. Prometrium), this drug has a relatively low oral bioavailability with a typical 200 mg dosing producing a C_{max} in the 5-10 ng/mL range. Due to first-pass hepatic metabolism, very high levels of metabolites including allopregnanolone and pregnanolone occur and can circulate as neurosteroids with strong potentiation of GABA_A receptors leading to the commonly reported side effects of dizziness, drowsiness, sedation, somnolence and fatigue. This factor really limits how high a dose of oral progesterone can be used. In regards to mucosal absorption approaches, both vaginal and rectal suppositories have been used. Tablet and capsule forms of progesterone for vaginal administration is available in the United States (US) but the 100 mg dose still only produces a C_{max} of approximately 10 ng/mL and would only be an option for female patients. While rectal suppositories can be used for either sex, C_{max} is generally lower (approximately 80% of what is achievable with comparable dose vaginal administration) and there is still some level of first-pass hepatic metabolism. In addition, no formulation has been approved by the FDA for use in the US via this route of administration. Finally, in regards to injection, both intramuscular (IM) and subcutaneous (SC) administration have been examined. Since progesterone is lipid-soluble, progesterone for IM injection have been primarily administered within an oil-based solution. While the IM route can achieve very high plasma drug levels and even has somewhat of a depot effect which could

permit less frequent dosing (up to 3 days between doses), it is often associated with moderate-to-severe injection site reaction and patients would typically not be able to self-administer this formulation. On the other hand, SC injection is now possible through an aqueous formulation developed by IBSA Institut Biochimique SA (Lugano, Switzerland). This formulation (marketed as Prolutex™ in Europe) dissolves the lipophilic natural progesterone as an aqueous solution containing β -cyclodextrin. This aqueous formulation of progesterone can be conveniently self-administered by patients and produces high systemic levels on the order of 20-40 fold higher than what is achievable with oral administration. The pharmacokinetics of aqueous SC progesterone is presented below (**Section 5.1**). Given these advantages, we have opted to use this formulation for SC injection in this current study.

4. Study Intervention/Investigational Agent

4.1 Description

Natural Progesterone

Chemical Name: pregn-4-ene-3, 20-dione (molecular weight 314.47, molecular formula $C_{21}H_{30}O_2$)

Other Names: Progesterone

Mechanism of Action: Progesterone is a progestogen, and an agonist of the nuclear progesterone receptors (PRs), the PR-A, PR-B, and PR-C [Kuhl, 2005]. In one study, progesterone showed EC_{50} values of 7.7 nM for the human PR-A and 8.0 nM for the human PR-B [Attardi et al. 2004]. In addition to the PRs, progesterone is an agonist of the membrane progesterone receptors (mPRs), including the mPR α , mPR β , mPR γ , mPR δ , and mPR ϵ [Guennoun 2020; Ryu et al. 2017]. It is also a potent anti-mineralocorticoid (antagonist of the mineralocorticoid receptor (MR)) [Rupprecht et al. 1993; Elger et al. 2003], as well as a very weak glucocorticoid (agonist of the glucocorticoid receptor) [Attardi et al. 2007; Lei et al. 2012].

Pharmacokinetics:

Graph/table of plasma progesterone levels after subcutaneous injection^a

[figure not shown]

Table 2. Main progesterone baseline-corrected pharmacokinetic parameters (mean \pm sd) calculated after subcutaneous administration of a Prolutex[®] single dose of 25, 50 and 100 mg. $n = 12$.

Pharmacokinetic parameter	25 mg	50 mg	100 mg
C_{max} (ng/mL)	57.8 \pm 13.6	103 \pm 24.5	235 \pm 62.6
T_{max} (h)	0.92 \pm 0.42	0.92 \pm 0.42	0.92 \pm 0.42
AUC_{0-t} (ng/mL/h)	338 \pm 91.6	729 \pm 228	1466 \pm 213
$AUC_{0-\infty}$ (ng/mL/h)	349 \pm 91.1	746 \pm 250	1490 \pm 213
$t_{1/2}$ (h)	13.1 \pm 7.1	17.2 \pm 5.1	17.6 \pm 5.8

AUC_{0-t} , area under the curve from time 0 to the last observed concentration time t ; $AUC_{0-\infty}$, area under the curve extrapolated to infinity; C_{max} , maximum serum concentration; T_{max} , serum peak concentration time, $t_{1/2}$, half-life.

^a [Cometti 2015]

Metabolism and Elimination: Progesterone is metabolized primarily by the liver largely to pregnanediols and pregnanolones. Pregnanediols and pregnanolones are conjugated in the liver to glucuronide and sulfate metabolites. Progesterone metabolites which are excreted in the bile may be deconjugated and may be further metabolized in the intestine via reduction, dehydroxylation, and epimerization.

The glucuronide and sulfate conjugates of pregnanediol and pregnanolone are excreted in the bile and urine. Progesterone metabolites are eliminated mainly by the kidneys. Progesterone metabolites which are excreted in the bile may undergo enterohepatic recycling or may be excreted in the feces.

The elimination half-life of the subcutaneous progesterone formulation (aq. for SC injection) is 13 to 18 hours. Pharmacokinetic assessments of this formulation will be determined for a limited number of recurrent GBM patients on this study to assure similar pharmacokinetic behavior compared with previous assessments of subcutaneous progesterone.

4.2 Drug/Device Handling

Drug Source: Subcutaneous progesterone; IBSA Institut Biochimique SA.

Formulation: Progesterone 25 mg/vial aqueous injection suspension.

Route of Administration: Subcutaneous (alternate over different sites).

Site of Storage: Winship Investigational Drug Service (IDS).

Storage and Stability: Store at 20°C to 25°C (68° to 77°F), and excursions of 15°C-30°C (59°-86°F) are permitted (see USP Controlled Room Temperature. Do not freeze nor refrigerate. The product should be protected from exposure to light.

Drug handling: Stored drug will be handled per the SOP of the Winship IDS. Once a dose level has been determined for a particular patient, the Winship IDS will prepare enough dose to allow dispensing of a two-week supply of drug for the subject. Instructions will be given to the patient or their designee/caretaker regarding the handling procedure and method of administration (instructed on daily subcutaneous administration by a licensed individual per Winship SOP 6.2) of the progesterone. The patient will need to return every two weeks to pick up their next medication supply.

IND Holder: [name], PhD (as the Sponsor-Investigator).

4.3 Accountability

The aqueous progesterone for injection (study drug) provided for this study will be used only as directed in the study protocol. The study drug will be provided by the company (IBSA Institut Biochimique SA, Lugano, Switzerland). Winship IDS personnel will account for all study drug. Drug accountability should be performed until the patient stops study treatment completely.

Study drug supplies must be kept in an appropriate, secure locked area and stored in accordance with the conditions specified on the labels. The Investigator, pharmacist, or designee must maintain an accurate record of dispensing the study drug in a Drug Accountability Log.

The Drug Accountability Log may record specifics to study drug dispensation such as:

- Records of product delivery, inventory, temperature monitoring, destruction, and return.
- Dosages prepared, time prepared, doses dispensed.
- Doses and/or vials destroyed.
- The Drug Accountability Log may be reviewed by the monitor during site visits and at the completion of the study.

Drug accountability may be noted by the internal monitor during site visits and at the completion of the study. Patients will be asked to return all unused study treatment and packaging on a regular basis, at the end of the study or at the time of study treatment discontinuation.

The study drug supply will be disposed of per Winship's Investigational Drug Service (IDS) SOP.

Compliance will be assessed by the investigator and/or study personnel at each patient visit and information provided by the patient and/or caregiver (collection of drug diary) will be captured in the Drug Accountability Form. This information must be captured in the source document at each patient visit.

Dose level for individual patients will be verified by two individuals authorized on study: the investigator or sub-investigator ordering the study drug and another licensed staff member, such as, Pharmacist (Pharm. D.), physician-investigator (M.D.), CRN, or Advanced Practice Providers (APP), and 2 weeks of drug at a time will be dispensed for patient to self-administer. The patient will be requested to maintain a medication diary of each dose of medication. The medication diary (**see Appendix 3**) will be returned to clinic staff every two weeks when patient returns for their next supply.

Dose changes and interruptions of study drug must be specifically documented in the patient source documents and eCRF.

5. Procedures Involved

5.1 Study Design

This clinical trial is a Phase 1 pilot study assessing the pharmacokinetics, safety/tolerability, and antitumor efficacy of aqueous injectable progesterone for the treatment of recurrent GBM (see Schema in **Section 1.2**).

Dose-Finding: Part 1 comprises the initial dose-finding phase of the study where 3+3 patients will potentially be enrolled and treated at each dose level (levels -1 to 1) to find the highest dose that is both safe and tolerable for eligible patients with GBM at 1st to 3rd recurrence. Subjects will receive aqueous progesterone for injection subcutaneously on a daily basis at the currently assessed dose level for up to 24 weeks unless the patient is discontinued prior to that time for one of the reasons specified below.

Cohort Expansion: Part 2 comprises the expansion phase of the study where a total of 20 patients will be treated at the highest dose identified to be safe and tolerable during Part 1 of the study. Subjects will receive aqueous progesterone for injection subcutaneously on a daily basis at the dose level determined in Part 1 of the study for up to 24 weeks unless the patient is discontinued prior to that time for one of the reasons specified below.

The study is divided into a Screening period, Treatment period, and End of Treatment (EOT) period.

During the Screening period patients will provide written informed consent to participate in the study before completing any protocol-specified procedures or evaluations not considered to be part of the patient's standard care. Procedures that were performed for standard of care prior to signing informed consent may be used for screening purposes (e.g., full physical exam) as long as the procedures were completed within the **14-day screening period** prior to initiation of progesterone therapy. After signing the ICF, patients will be evaluated for entry criteria during the screening period within **14 days** before administration of study drug(s). Rescreening after screen failure will be allowed.

For the Treatment period, patients will be treated with progesterone for up to 24 weeks unless there is unacceptable toxicity, death, disease progression per protocol-specified criteria, Investigator's decision to discontinue treatment, the patient withdraws consent, is lost to follow-up, or Institution decides to terminate the trial.

Patients with progressive disease (PD) per protocol-specified criteria but with otherwise stable or improved performance and clinical status may continue to be treated in the event of a perceived benefit per Investigator. Patients who are tolerating the drug with stable disease (SD) or better after 24 weeks of therapy may be considered for compassionate use continuation on a case-by-case basis after discussions between the patient, treating physician and the study supporter (IBSA Institut Biochimique SA, Lugano, Switzerland). It is at the discretion of the Investigator to continue treating patients in this circumstance as long as IBSA agrees to continue to provide drug until unacceptable toxicity, disease progression or patient withdrawal. Followup evaluations under these circumstances will be considered standard-of-care at the discretion of the patient's treating physician.

The EOT period would last for 4 weeks after drug discontinuation at which point the end-of-study (EOS) visit would occur where final Adverse Event (AE) documentation and other study-required assessments are performed. Further assessment of progression or death for determination of PFS and OS will be based on review of records obtained after this point on a retrospective basis where additional treatments and followup intervals will be at the discretion of the patient's treating physician.

5.2 Dosing and Administration

Formulation: An aqueous formulation of natural progesterone complexed with 2-hydroxypropyl- β -cyclodextrin (Subcutaneous progesterone; IBSA Institut Biochimique SA, Lugano, Switzerland) will be used. An IND for this formulation will be cleared by the FDA and cross-referenced to support the present study.

Route of administration: Each dose (25-75 mg) will be given daily by subcutaneous injection using a tuberculin syringe with sterile technique. The site of injection will rotate along different sites (standard locations including abdomen, thigh) based on patient preference with at least 1 day break between reinjection of a particular site. Each injection will consist of 25-50 mg of drug in 1-2 ml with multiple injections to be used if higher doses of drug are called for per study.

Timing of administration: Drug will be injected subcutaneously at about same time in the AM \pm 3 hours each day.

Pharmacokinetic assessment (only 1st 3 patients at each dose cohort): Will only be done on the first three patients at each dose level cohort. Assessment time points will be start on day 1 of treatment. Blood draws will be performed immediately prior to drug administration (by subcutaneous injection). Subsequent blood samples will be obtained at 30 minutes, 1 hour, 2 hours, 4 hours, 6 hours and 8 hours following progesterone injection. One additional time point will be performed on day 8 just prior to drug injection on those days.

Dose Finding Phase (Part 1):

Patients will be enrolled sequentially and will follow a 3+3 design. The dose levels that will be potentially used are on the following table:

Dose Level	Dose of aqueous natural progesterone for injection (mg)
Level -1	25
Level 0	50
Level 1	75

Dosing will start at Dose Level 0 and will escalate or de-escalate according to the following rules:

Dose Level -1

- 0 of 3 with DLT → **expand Level -1 to 20 patients**
- 1 of 3 with DLT → 3 more at Level -1
 - 1-2 of 6 with DLT → **expand Level -1 to 20 patients**
 - 3-4 of 6 with DLT → consider stopping study
- 2-3 of 3 with DLT → consider stopping study

Dose Level 0

- 0 of 3 with DLT → move to Level 1
- 1 of 3 with DLT → 3 more at Level 0
 - 1 of 6 with DLT → move to Level 1
 - 2 of 6 with DLT → **expand Level 0 to 20 patients**

3-4 of 6 with DLT → drop to Level -1
2-3 of 3 with DLT → drop to Level -1

Dose Level 1

0 of 3 with DLT → **expand Level 1 to 20 patients**
1 of 3 with DLT → 3 more at Level 1
1-2 of 6 with DLT → **expand Level 1 to 20 patients**
3-4 of 6 with DLT → **expand Level 0 to 20 patients**
2-3 of 3 with DLT → **expand Level 0 to 20 patients**

During the dose finding phase of the study, a treatment will be considered safe/tolerable if no DLT defined as \geq grade 3 toxicity during the first 4 weeks drug therapy not clearly due to the underlying disease or extraneous causes with exceptions as noted in **Section 5.3**. After treatment initiation of up to 6 patients at a dose level and continuation for a minimum of 4 weeks with AE assessment, enrollment to the next (higher or lower) dose level as determined by the rules will only start after data is presented to the Winship Data Safety Monitoring Committee (DSMC) and final approval is obtained for starting the next dose level.

Dose escalations will be reviewed by the Winship Data Safety Monitoring Committee (DSMC) (per Winship SOP 7.9 Dose Escalation Determinations for Sponsor-Investigator or Investigator Initiated Studies). The PI or designee will provide an update on all relevant safety data of patients entered to a dose level to the DSMC when dose escalation is planned. Upon obtaining approval from the DSMC, dose escalation can proceed.

Dose Expansion Phase (Part 2):

The purpose of cohort expansion is to gather additional safety and tolerability information, and evaluate the efficacy of aqueous natural progesterone for injection at the dose determined by the Dose Finding Phase of the study.

The PI or designee must provide the DSMC a report outlining the overall enrollment and path to decision for the escalation dose(s) selected.

Continuous evaluation of toxicity events in the cohort expansion will be performed throughout enrollment in the expansion cohort. If, at any time, the aggregate rate of treatment-related toxicities meeting DLT criteria exceeds 33% across all subjects treated in the expansion cohort, the findings will be discussed and further enrollment may be interrupted. Depending on the nature and grade of the toxicity and after assessing the risk:benefit ratio, a new dose(s) for all cohorts may be initiated at a previously tested lower dose level, or at a dose level intermediate to previously tested lower dose levels.

In addition to continuous evaluation of toxicity, there will be one interim efficacy evaluation for futility. It is known that random ineffective therapies for recurrent GBM may still produce a response rate of 10%. Therefore, the overall response rate (ORR) for first 10 patients (1/2 of planned expansion cohort size) that undergo treatment with the subcutaneous progesterone at the final dose from the dose finding phase of the

study will be determined. If the ORR at the 8 week assessment time point is 20% (2 of 10) or greater, then the study will be declared potentially non-futile and enrollment of the full expansion cohort (N=20) will proceed. If the ORR at this time point is 10% (1 of 10) or less, then the study will be declared futile and further enrollment will be aborted. If the study is declared futile at this interim analysis, new enrollment will be discontinued but any patients that is still on therapy at that time will be allowed to continue therapy as long as they meet criteria to continue therapy as defined in Section 8.1 (e.g. continue to not have protocol-specified progressive disease).

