- To determine if the absolute values or changes in the level of serum biomarkers (see **Section 5.7** for specific biomarkers) correlates with response to daily subcutaneous natural progesterone. This will be examined for both expansion dose patient and all patients as separate analyses. Each of these serum biomarkers will be quantitated at the specific time points (pre-treatment and 4 weeks) with specific levels and changes in levels recorded. These results will be correlated with response assessment using two sample t-tests or Mann-Whitney U tests, where appropriate.
- To determine the quality-of-life (QOL) by validated instruments of eligible patients with recurrent GBM. This will be examined for both expansion dose patient and all patients as separate analyses. Serial QOL assessments will be determined in patients and compared with historical cohorts to determine whether there is any difference in patients treated with subcutaneous progesterone for recurrent GBM. Linear mixed effects models will be applied to model the repeatedly measured score from each assessment and/or test over time. We hypothesize that response to progesterone will correlate with positive effects on the temporal changing patterns in the scores on the QOL assessments. We will follow the recent guidelines of the American Statistical Association on reporting p-values and their meaning [Wasserstein and Lazar 2016; Wasserstein et al. 2019]

Safety assessment:

Adverse event stopping rule including interim analysis: Safety assessments will be performed throughout treatment, at weekly intervals during the 1st 4 weeks and at the beginning of every 4 weeks interval thereafter until patient comes off study. In the dose finding phase, stopping rules are described above. Besides the toxicity assessment of 3-6 patients at a dose level in the dose finding phase, toxicity will be assessed during the dose expansion phase on an ongoing basis. If, at any time, the aggregate rate of treatment-related toxicities meeting DLT criteria exceeds 33% across all subjects treated in the expansion cohort, the findings will be discussed and further enrollment may be interrupted. Depending on the nature and grade of the toxicity and after assessing the risk:benefit ratio, a new dose(s) for all cohorts may be initiated at a previously tested lower dose level, or at a dose level intermediate to previously tested lower dose levels.

15.2 Data/specimens:

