The Data and Safety Monitoring Committee (DSMC) of the Winship Cancer Institute will provide oversight for the conduct of this study. The DSMC functions independently within Winship Cancer Institute to conduct internal monitoring functions to ensure that research being conducted by Winship Cancer Institute Investigators produces high-quality scientific data in a manner consistent with good clinical practice (GCP) and appropriate regulations that govern clinical research. Depending on the risk level of the protocol, the DSMC review may occur every 6 months or annually. For studies deemed High Risk, initial study monitoring will occur within 6 months from the date of the first subject accrued, with 2 of the first 5 subjects being reviewed. For studies deemed Moderate Risk, initial study monitoring will occur within 1 year from the date of the first subject accrued, with 2 of the first 5 subjects being reviewed. Subsequent monitoring will occur in routine intervals per the [Winship Data and Safety Monitoring Plan \(DSMP\)](#).

The DSMC will review pertinent aspects of the study to assess subject safety, compliance with the protocol, data collection, and risk-benefit ratio. Specifically, the Winship Cancer Institute Internal Monitors assigned to the DSMC may verify informed consent, eligibility, data entry, accuracy and availability of source documents, AEs/SAEs, and essential regulatory documents. Following the monitoring review, monitors will provide a preliminary report of monitoring findings to the PI and other pertinent individuals involved in the conduct of the study. The PI is required to address and respond to all the deficiencies noted in the preliminary report. Prior to the completion of the final summary report, monitors will discuss the preliminary report responses with the PI and other team members (when appropriate). A final monitoring summary report will then be prepared by the monitor. Final DSMC review will include the final monitoring summary report with corresponding PI response, submitted CAPA (when applicable), PI Summary statement, and available aggregate toxicity and safety data.

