The DSMC will render a recommendation and rating based on the overall trial conduct. The PI is responsible for ensuring that instances of egregious data insufficiencies are reported to the IRB. Continuing Review submissions will include the DSMC recommendation letter. Should any revisions be made to the protocol-specific monitoring plan after initial DSMC approval, the PI will be responsible for notifying the DSMC of such changes. The Committee reserves the right to conduct additional audits if necessary.

The PI or designee must provide the DSMC a report outlining the overall enrollment and path to decision for the escalation dose(s) selected.

Additional points in regards to the DSMP specifically for this study:

- After the first subject has enrolled, monthly research meeting will be held by the PI along with selected members of the study team to review toxicity and efficacy data as they are acquired.
- AEs (including SAEs) will be recorded based on planned assessment time points by the CRC and assessed by the PI/sub-investigators according to SOP. These will then be reviewed on an ongoing basis at the monthly research meeting with reports to the DSMC at appropriate times (e.g. to initiate next dose level).
- Oversight of the study team will be carried out at neuro-oncology working group meeting and will include random checks of CRFs/charts.
- Study team will be trained on study procedures at a study initiation meeting prior to study opening. Changes to the study (e.g. Study Amendments) will be communicated to the entire study team by e-mail with documentation that team members acknowledgement their understanding of the changes.

17. Provisions to Protect the Privacy Interests of Participants

Participants will be assured of their voluntary participation in the study, their choice to answer or not answer any question, and the protocol for maintaining confidentiality.

Participant confidentiality is strictly held in trust by the participating investigators, their staff, and the sponsor(s) and their agents. This confidentiality is extended to cover testing of biological samples and genetic tests in addition to the clinical information relating to participants. Therefore, the study protocol, documentation, data, and all other information generated will be held in strict confidence. No information concerning the study or the data will be released to any unauthorized third party without prior written approval of the sponsor.

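### Crossing the 33% toxicity limit in expansion obliges only a discussion: the pause and the dose reduction are optional, and no decision-maker or DSMC referral is named

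*Combined protocol and SAP*

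**What the plan says.** The limit appears in section 5.2 (Dose Expansion Phase) and again in section 15.1 (Safety assessment), where it comes under the label "Adverse event stopping rule including interim analysis". It applies at any time that the "aggregate rate of treatment-related toxicities meeting DLT criteria exceeds 33" per cent of subjects treated in the expansion cohort. The consequence is the same in both places: "the findings will be discussed and further enrollment may be interrupted". The next sentence adds that, after a risk-benefit assessment, a lower or intermediate dose may be started. Neither section says who holds the discussion or who decides.

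Other provisions bear on the point:

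- **Dose finding (5.2).** "enrollment to the next (higher or lower) dose level as determined by the rules will only start after data is presented" to the DSMC and its approval obtained.
- **Futility (5.2, 15.1).** With 1 response or none among the first 10 patients, further enrolment stops. This rule is binding.
- **Study-team review (section 16).** A "monthly research meeting will be held by the PI along with selected members of the study team to review toxicity and efficacy data", with "reports to the DSMC at appropriate times (e.g. to initiate next dose level").
- **Routine DSMC review (section 16).** "Depending on the risk level of the protocol, the DSMC review may occur every 6 months or annually".
- **Individual patients (5.4).** Drug is withheld for most grade 3 or higher toxicity. It restarts at half dose unless the cause is clearly the disease or something extraneous.
- **Entry to expansion (5.2).** At Levels 1 and -1, "1-2 of 6 with DLT" leads to expansion; at Level 0, 2 of 6 does.
- **Cohort size (15.1).** The 20 expansion patients include dose-finding patients treated at that dose.

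**The concern.** A rule presented as a stopping rule should say what stops, and who may restart it. Here a team could follow both sections to the letter, exceed the limit, hold a discussion and keep enrolling at the same dose, without the DSMC having been told. Most exposure at the selected dose happens in this phase: 14 to 17 of the 20 patients are still to enrol when it opens. The patients at risk are those not yet enrolled, and the individual holds in section 5.4 do nothing for them. Judgement about the nature and grade of events is a good reason to leave the next step open. It is not a reason to keep enrolling while that judgement is being made.

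The numerical limit has a separate flaw. Because 2 of 6 is 33.3%, a dose allowed into expansion can already be over a literal 33% limit before any further patient is treated.

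**Working it through.** The plan gives no operating characteristics for this limit, so there is no stated figure to reproduce.

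**Inputs from the documents.** The cohort is 20 including dose-finding patients (15.1). Expansion can open from 0 of 3, 1 of 6 or 2 of 6 (5.2). Accrual is 1-2 patients per month (section 9). DSMC review is every 6 or 12 months (section 16).

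**Assumptions.** The DLT rate p is taken from 5% to 40%, because the documents state none. One dose level is considered alone. The limit is read as more than one third (3x > n for x patients with a DLT among n). Each DLT is known at once, and the futility stop is ignored.

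**Patients exposed.** Still to enrol: 20 - 6 = 14 to 20 - 3 = 17. Between six-monthly reviews: 6 × 1 to 6 × 2 = 6 to 12. Between annual reviews: 12 × 1 to 12 × 2 = 12 to 24, capped at the 14-17 remaining.

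**Passing 3+3.** P(0/3) = (1-p)³; P(1/6) = 3p(1-p)² × (1-p)³; P(2/6) = [3p(1-p)²]².

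**Crossing afterwards.** Exact sequential binomial calculation from each starting point, checked after every patient up to n = 20.

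| p | P(pass 3+3) | cross from 0/3 | from 1/6 | from 2/6 | pass and cross | cross, given expansion |
|---|---|---|---|---|---|---|
| 5% | 0.992 | 0.004 | 0.003 | 0.105 | 0.005 | 0.005 |
| 10% | 0.965 | 0.019 | 0.019 | 0.222 | 0.031 | 0.03 |
| 20% | 0.856 | 0.130 | 0.124 | 0.479 | 0.162 | 0.19 |
| 30% | 0.689 | 0.381 | 0.351 | 0.720 | 0.324 | 0.47 |
| 40% | 0.496 | 0.682 | 0.632 | 0.886 | 0.372 | 0.75 |

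Worked line at 40%: P(pass) = 0.216 + 0.093 + 0.187 = 0.496. Joint = 0.216 × 0.682 + 0.093 × 0.632 + 0.187 × 0.886 = 0.372. Given expansion: 0.372 / 0.496 = 0.75.

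**Still to enrol when crossed at 40%.** The mean is 10.1 if each DLT is known at once, 9.1 if one more patient enrols before it is known, and 8.2 if two do.

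**The entry conflict.** 2/6 = 0.333 > 0.33, so the literal limit is exceeded at entry. Under more than one third, 3 × 2 = 6 is not greater than 6, so 2 of 6 does not trigger. The smallest triggering counts are 2 of 4-5, 3 of 6-8, 4 of 9-11, 5 of 12-14, 6 of 15-17 and 7 of 18-20.

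**The case against.** The strongest reply is that this is a small pilot in which toxicity decisions are deliberately left to judgement. Dose finding does the same: at Level -1, even 2-3 of 3 or 3-4 of 6 DLTs lead only to considering whether to stop the study. That is correct, and it weakens the contrast with the binding futility rule. It does not turn the expansion limit into a stopping rule.

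Second, oversight exists. Toxicity is evaluated continuously, the study team meets monthly, and SAEs go to the supporter within 24 hours and are assessed for reporting to the DSMC. The DSMC's remit covers safety and risk-benefit, and it can order extra audits. The example given for DSMC reporting is not exhaustive, and a crossing would be a natural occasion. A reader might infer that toxicity in expansion goes unwatched; the documents do not support that. What stands is narrower: none of these provisions requires a cohort pause or prompt independent review when the limit is crossed.

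Third, the DSMC approval requirement mentions moves to a lower dose. But it refers to moves under the 3+3 rules, and section 15.1 places it under Part 1. The institutional monitoring plan and SOP 7.9 are cited but not included, so an escalation duty there cannot be excluded. SOP 7.9 is cited for dose escalation.

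Fourth, the drug may be well tolerated. Section 13 lists mainly administration-site, breast and vulvo-vaginal reactions, though in a different population. A crossing would then be rare.

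Fifth, the counts of remaining patients are on the high side. The 28-day DLT window is stated for dose finding, while treatment lasts up to 24 weeks, so later events would mean later crossings. At the plan's 10% response rate for ineffective therapy, futility stops enrolment at 10 patients with probability 0.9¹⁰ + 10 × 0.1 × 0.9⁹ = 0.74. Both points stand.

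**Conclusion.** The point holds as a weakness in the rule's wording. Exceeding 33% obliges a discussion and nothing more; the pause and the dose reduction are both optional, and no decision-maker or DSMC referral is attached. It would be wrong to say that a pause is the only further step provided for, because a lower or intermediate dose is also allowed.

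A reader might also infer that the limit is likely to be crossed. That is fair only near an assumed 40% DLT rate (0.75 given expansion). It is about even at 30%, 0.19 at 20% and 0.03 at 10%. These figures treat one level alone, whereas at starting Level 0 a result of 0 of 3 or 1 of 6 leads first to Level 1. The mean of about 10 patients still to enrol at 40% is best read as an upper figure.

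The 2 of 6 conflict depends on dose-finding patients counting toward the limit, which section 15.1 implies but does not state for this rule. The likely intent is more than one third, which removes it. Given the partial safeguards, this is a cheap improvement rather than a critical defect.

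**What to change.** Replace the consequence in sections 5.2 and 15.1 with:

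*If more than one third of all patients treated at the expansion dose, including dose-finding patients, have had a treatment-related toxicity meeting DLT criteria (2 of 4-5, 3 of 6-8, 4 of 9-11, 5 of 12-14, 6 of 15-17, 7 of 18-20), new enrolment is suspended and the data are sent promptly to the DSMC. Enrolment resumes, at the same or a lower dose, only with DSMC approval, and the DSMC sets the next review point.*

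The event definition is unchanged, and judgement about the next step is kept.

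The cost is a short text change in two places and some unscheduled reviews by an existing committee. False alarms will occur: at a 20% DLT rate, in 12-13% of expansions from 0 of 3 or 1 of 6 and 48% from 2 of 6. Each costs a short pause, not the trial.

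Against the literal 33% cut, sensitivity at a 40% rate falls from 75% to 68% from 0 of 3, and from 70% to 63% from 1 of 6. In return, the joint chance of passing 3+3 and raising a false alarm at 20% falls from 0.29 to 0.16. If every fresh crossing needed review, simulation gives about 1.6-1.7 reviews per crossing trial at 40%. Letting the DSMC set the next review point limits that.
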